Setting and population: The Klipfontein sub-district is a resource-limited, densely populated, high HIV disease burden areas in Cape Town. Newly diagnosed COVID19 cases will be identified from two sources: screening conducted in DTHF mobile screening units and local public sector clinics. Consecutive cases (n=120 and households) will be invited to participate. After enrolment, the household will be randomised to the STOPCOV intervention or enhanced usual care messaging.

Design: A cluster randomised controlled study with longitudinal follow up of SARS-CoV-2 infection in 120 households which have newly diagnosed positive cases. The index cases and their HHC will be invited and enrolled after informed consent. Baseline surveys and SARS-CoV-2 screening (PCR and IgM/IgG serology) and then weekly SARS-CoV-2 screening (PCR and serology) of HHC will occur at 0, 1, 2, 3 and 4 weeks. The households will be randomized to an intensified COVID19 infection mitigation intervention (n=60) administered by CHWs vs standard messaging currently being provided (n=60).

Analysis: The proportion of SARS-CoV-2 transmission from index cases to HHC over 4-week period will be calculated. The proportion of symptomatic and asymptomatic SARS-CoV-2 infection in a high density, low resourced community will be described. The impact of the STOPCOV intervention by assessed by measuring transmission, and clinical outcomes, in households randomised to intervention vs standard of care. A process evaluation will explore the feasibility, acceptability and contextual factors impacting the STOPCOV intervention delivery.

TRaCE Schema
Questions: 1 What is the transmission pattern (Ro number and timing of infection) of SARS-CoV-2 in a household in which a COVID-19 case has been identified in a low-income, high density community in Cape Town? 2 What is the burden of symptomatic versus asymptomatic SARS-CoV-2 cases in a high HIV/ TB disease burden setting in Cape Town, South Africa? 3 Can an intensified, infection mitigation intervention reduce the transmission in a household setting, improve clinical outcomes and reduce psychosocial impact of a COVID19 diagnosis?
Objective: The overarching objective of this protocol is to understand and mitigate household transmission of SARs-CoV-2 infection in a low income, high density community setting.

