Aims: Specific Aim 1: To measure frequency and timing of transmission of SARS-CoV-2 to household contacts. The proportion of patients and household contacts who have symptoms vs asymptomatic disease will also be measured. Specific Aim 2: To investigate the effect of an intensive infection mitigation intervention (STOPCOV) administered by lay health care workers on the household transmission of SARS-CoV-2, clinical outcomes and psychosocial functioning.
Design: The study design is a type 2 hybrid cluster (household) randomised controlled trial, with outcomes assessed on index patients and their household contacts (Fig 1). 120 consecutively newly diagnosed index patients (GeneXpert SARS-CoV-2 PCR) and up to 8 household contacts will be invited to participate in the trial as part of the prospective observational study evaluating transmission and symptoms. After completing consent, households will be randomised in a 1:1 ratio in blocks of 10 (60 households per group; 360 patient and household contacts per group).
Study setting and population: Klipfontein is a resource-limited, densely populated, high HIV/TB disease burden areas in Cape Town. Newly diagnosed COVID19 cases will be identified from two sources: screening conducted in DTHF mobile screening units and local public sector clinics working closely with DTHF. Consecutive cases (n=120 cases and households) will be invited to participate in the randomised trial and prospective longitudinal follow up of up to ~6 -8 household contacts. The contacts will be followed up after informed consent to SARS-CoV-2 screening, symptomatic questionnaires weekly up to 1 month.
Study size: We will enrol n=120 SARS-CoV-2 positive and n=~6 their household contacts (n=~720).

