Process: Newly diagnosed SARS-CoV-2 index patients will be identified and recruited from a mobile clinic and local community clinics conducting SARS-CoV-2 testing. Index cases and their households will be invited to enroll. After enrolment, the household will be randomised to the infection mitigation intervention or enhanced usual care messaging. Baseline demographic, household characteristics questionnaire will be administered, and each household occupant invited to participate. Following consent procedures, household contacts (HHC) will be screened at baseline and weekly for 4 weeks for evidence of COVID infection. Specifically, the research team will conduct SARS-CoV-2 GeneXpert PCR testing and antibody serology. They will collate self- administered daily symptom checks on a weekly basis. Six months after a positive SARS-CoV-2 antibody, the study nurse will visit the participant household to conduct SARS-CoV-2 serology to assess for the presence of antibodies.
Duration: We will recruit 120 households over 1-3 months. We will initiate a prospective longitudinal follow up of the household contacts of each case for 4 weeks in each case.
Analysis: Calculate proportion of SARS-CoV-2 transmission from index cases in each household over 4- week period. Describe the proportion of symptomatic and asymptomatic SARS-CoV-2 infection in a high density, low resourced community. Investigate the impact of the infection mitigation intervention by comparing Ro number in households randomised to intervention vs standard of care. Secondary outcomes for the trial will include clinical outcomes (hospitalisations, death), linkages to care for people, psychosocial functioning and stigma.

Background

South Africa currently has the largest COVID19 epidemic in Africa, with >205,721 cases reported in all nine Provinces (*COVID-19 South African Coronavirus News and Information Portal*, n.d.). The South African Department of Health has reported more than 3310 deaths of individuals infected with severe acute respiratory syndrome coronavirus-2 (SARS-CoV-2), the cause of coronavirus disease (COVID-19) to date (Karim, 2020). As screening and testing is scaled up, South African healthcare facilities are preparing for the mitigation stage in the epidemic, wherein people with severe COVID-19, mostly adults, may require hospitalization, and intensive care (Karim, 2020).

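### Could household contacts be recruited after their household's arm is known, because the Protocol does not fix the order of consent and randomisation?

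*Protocol*

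**What the plan says.** The Process paragraph of the TRaCE Schema (Protocol) makes four statements in this order:

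- The household as a whole is approached: "Index cases and their households will be invited to enroll"
- Once enrolled, the household is allocated to one of the two arms.
- A survey and an approach to individual occupants come next: "Baseline demographic, household characteristics questionnaire will be administered, and each household occupant invited to participate"
- Contacts who have consented are then tested, first at baseline and afterwards each week to week 4.

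The TRaCE summary (Protocol), under Setting and population, has: "After enrolment, the household will be randomised to the STOPCOV intervention or enhanced usual care messaging". Under Design it has "The index cases and their HHC will be invited and enrolled after informed consent". A sentence on the testing schedule follows, and then "The households will be randomized to an intensified COVID19 infection mitigation intervention (n=60) administered by CHWs". The Overview in SAP section 3 repeats this Design paragraph almost word for word.

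The Design row of the Schema and the Design section under Approach (Protocol) both state "After completing consent, households will be randomised in a 1:1 ratio in blocks of 10". The same sentence stands in SAP section 3, Randomization and stratification.

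No readable text says whether baseline PCR and serology are taken before the arm is revealed.

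**The concern.** The household is randomised, but the Aim 2 primary endpoint is measured in its contacts. Under SAP 7.1 a contact becomes a new case only relative to a negative baseline test. If contacts learned their household's arm before deciding whether to join, the two arms could hold different kinds of contacts. If baseline samples were taken after the intervention had begun, the at-risk set itself could differ by arm.

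The analysis would not repair this. Intention-to-treat in SAP section 5 is defined by household, and a frailty term allows for correlation within households. Neither recovers people who never consented. SAP 6.1 plans to report numbers screened and enrolled, but does not say that invited contacts will be counted by arm, so unequal uptake might not be visible.

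The Process paragraph appears to describe exactly this order. The arms also differ in ways a household would notice: Table 1 of the Protocol gives StopCov households a community health worker assessment at baseline and scheduled telephone support.

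**Working it through.** The question is one of sequence. No figure in the plan depends on it, so the check sets the texts side by side.

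**1. What each place says about order**

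| Place | Order suggested | Whose consent |
|---|---|---|
| Schema, Process | household invited, enrolled, randomised; then occupants invited, contacts consented and tested | contacts' consent mentioned after randomisation |
| Summary, Setting and population | enrolment, then randomisation | not stated |
| Summary, Design; SAP 3, Overview | index cases and contacts enrolled after consent; randomisation mentioned later | index cases and contacts |
| Schema, Design; Approach, Design | consent, then randomisation | preceding sentence names index patients and up to eight contacts |
| SAP 3, Randomization and stratification | consent, then randomisation | not stated there; the Overview names both groups |

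Only the first row points to recruiting contacts after allocation, and it does so only if its sentences are in time order.

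**2. Is sentence order a reliable guide to time?** In the summary's Design paragraph and the SAP Overview, the sentence before randomisation covers tests at weeks 0, 1, 2, 3 and 4. As a timeline, households would be randomised after week 4. The Protocol has health workers following StopCov households daily for the first two weeks and three times a week up to week 4, so that reading is impossible. These paragraphs list procedures; they do not narrate them. For the same reason, the summary's mention of baseline screening before randomisation is not evidence that samples come first.

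**3. Does the Process paragraph contradict the rest even on its own terms?** It invites households as well as index cases before the enrolment that precedes randomisation. The later sentence inviting each occupant can be read as spelling out that step. It can also be read as a second, individual invitation. The paragraph does not decide between them.

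**4. Does the cap of eight contacts add an opening for selection?** The Protocol's Population and Sample paragraph expects 6 to 8 occupants per household. Less the index case, that is 6 − 1 = 5 to 8 − 1 = 7 contacts. If the 6 to 8 is taken as contacts, as the same paragraph also allows, the maximum is 8. On either reading the cap would seldom bind.

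**5. Would arm knowledge give contacts a strong reason to join or refuse?** Both arms receive baseline and weekly testing, masks and sanitiser, and the printed PACK Home volumes. Both receive R150 at the baseline and final visits. Research staff collect the samples and assess outcomes; community health workers deliver the intervention. This does not establish blinding, but most of what taking part offers is common to both arms.

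**6. Can the possible bias be sized?** That would need contact participation and baseline positivity by arm. The documents give neither, so no range can be derived from them.

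**The case for a change.** The strongest opposing case is that the consent-first reading is an inference. No sentence requires every contact to have consented before the household is randomised, and none times the baseline samples against allocation. Table 1 also places the StopCov household assessment at baseline, without saying whether it comes before or after sampling. Table 2 does not help: as extracted it has no randomisation row, and its columns may be broken. Writing down one sequence and adding a table of contacts invited, consented and tested by arm would cost little.

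Part of this stands. The timing of baseline samples is unstated in the readable text, the Process paragraph is untidy, and late consent, if it occurred, could matter. But the study-flow diagrams in both documents were not available and may show the order, so the gap cannot be called a gap in the plan. A participant-flow table is reasonable reporting practice. SAP section 3 already names the randomisation list and the study database as data sources, so analysts can count enrolled contacts by arm without an amendment. Counts of invited contacts would depend on what the household tracing data hold.

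**Conclusion.** This is a loosely worded paragraph and a missing detail of sequence, not a design that recruits contacts after allocation. The Protocol's Design sections and the SAP are most naturally read as consent of index cases and contacts followed by randomisation, and a trial run that way gives a sound comparison. No stated rule, number or analysis is shown to produce a wrong result. Tidying the paragraph would be an editorial courtesy.

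The size and direction of any bias are unknown, and none is demonstrated. The conclusion assumes that staff follow the consent-then-randomise statement and that the unseen diagrams do not contradict it. If trial records showed contacts routinely consented after the arm was disclosed, the question would need to be reopened.

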With the advent of COVID19, the mobile services have added COVID testing to the suite of screening tests and has been conducting testing in partnership with the provincial health services since the beginning of April 2019. During the first three months of the pandemic the strategy had been to test all symptomatic individuals identified in a door to door community-based approach. Testing teams linked to the mobile and under armed police protection have been set up in “hotspots” in which a known COVID case has previously been identified. Community health care workers are trained to sweep through the immediate community administering a symptom questionnaire whilst community education via loud hailing is conducted. After completing a symptom questionnaire administered by community health workers, symptomatic individuals or people who have had known contact with a COVID case are screened by a clinician for symptoms and if confirmed, have been invited to undergo nasal swabbing in an outdoor gazebo linked to the mobile by a trained clinician. This has been done safely and with a reasonable yield. To date, the case fatality rate (CFR) is 354 per million in the Western Cape, which is over 7 times higher than the national mortality rate of 49 per million (<https://www.totalanalysis.com/187>). The CFR is projected to be 700 per million in the Klipfontein region (Timeslive, 2 July 2020).

These services have therefore already shown to be ideal for strategically identifying and following up cases and contacts of SARS-CoV-2 and triaging patients to quarantine, isolation, and hospital care as appropriate. The overall objective of this proposal is to understand and mitigate the transmission of SARS-CoV-2 in high density townships. We plan to do this by establishing the Ro number for SARS-CoV-2 in low-income high-density households, and evaluating the effect of a lay health worker administered risk mitigation strategy on transmission, clinical outcomes and psychosocial functioning compared with enhanced usual care.

Approach:

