Overall Objective: The overarching objective of this protocol is to understand and mitigate household transmission of SARS-CoV-2 infection in a low income, high-density community setting. Data over an 8-month period will be used to determine the Ro for SARS-CoV-2 infection, the rate of symptomatic disease and the impact of a lay health care worker administered infection mitigation intervention (STOPCOV) in low income, high-density communities in South Africa.

Specific Aim 1: To measure frequency and timing of transmission of SARS-CoV-2 to household contacts. The proportion of patients and household contacts who have symptoms vs asymptomatic disease will also be measured.

Specific Aim 1 Endpoints: SARS-CoV-2 transmission will be monitored using nasopharyngeal swabs for SARS-CoV-2 PCR and serology (IgM/IgG) assays in all HHC weekly for 1 month. Symptom checklists will be completed daily and collated weekly for each HHC.

Specific Aim 2: to investigate the effect of an intensive infection mitigation intervention known as STOPCOV administered by lay health care workers, compared with enhanced usual care, on SARS-CoV-2 household transmission.

Specific Aim 2 Primary Endpoint: The proportion of transmissions to HHC in the households of COVID cases assigned to the infection mitigation intervention arm compared with the households in the enhanced usual care (EUC) arm.

Population and Sample: We will consecutively recruit n=120 SARS-CoV-2 positive index patients 12 years and older. The index patients will be identified from referrals from associated public sector clinic screening in a high-density community in Cape Town. Each household is estimated to have 6-8 occupants. We will invite HHC (n=~6-8) household contacts of each of the index patients (n=~720).

Duration: The study will be conducted for eight months from June 2020 and last until Jan 2021.

[figure not shown]

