Setting: The study will be conducted in KMP. The community is a resource-limited, densely populated, high HIV/TB disease burden area in Cape Town. The DTHF Tutu Tester Mobile Clinics offer mobile HIV testing days in various locations in KMP. Specifically, there are four high HIV disease burden communities in the district; Philippi (population n=200,803), Crossroads (n=36,043), Gugulethu (n=98,468) and Nyanga (n=57,996). In addition to our well-established relationship with community organisations such as an independent advisory board, we have provided HIV testing services and linkage to treatment from the mobile clinic since 2008 and are currently partnering with the KMP subdistrict health team in providing COVID screening and testing. Given our long-term relationship with and service in the community, our relationships with the Provincial Department of Health, and our experience with the research platforms, it is feasible for us to successfully execute the proposed

research. The mobile clinic team will provide a screening service and SARS-CoV-2 polymerase chain reaction (PCR) testing with the GeneXpert or courier samples to accredited laboratories and rapid testing with the SARS-CoV-2 antibody COVID-19 IgG/IgM Rapid Test Device. Additionally, the mobile clinic team will offer screening for HIV, TB, STI and chronic diseases (e.g. diabetes, hypertension, and obesity).

Design: A cluster randomised controlled study with longitudinal follow up of SARS-CoV-2 infection in 120 households which have newly diagnosed SARS-CoV-2 positive cases. The index cases and their household contacts will be invited to participate in the study after informed consent. Baseline surveys and screening and then weekly screening of HHC will occur (Table 1). These household contacts will be tested at 0, 1, 2, 3 and 4 weeks.

The study design is a type 2 hybrid cluster (household) randomised controlled trial, with outcomes assessed on index patients and their household contacts (Diag 1). 120 consecutively newly diagnosed index patients (GeneXpert SARS-CoV-2 PCR) and up to 8 household contacts will be invited to participate in the trial as part of the prospective observational study evaluating transmission and symptoms. After completing consent, households will be randomised in a 1:1 ratio in blocks of 10 (60 households per group; 360 patient and household contacts per group).

Diagram 1: Study flow

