A mixed methods process evaluation will explore acceptability, feasibility and contextual factors impacting intervention delivery guided by the Consolidated Framework for Implementation Research. Qualitative data collection during the first 4 weeks will be curtailed to minimise exposure of research staff completing qualitative interviews (high risk for COVID-19 transmission) and will be limited to observation of CHW training and up to 5 initial CHW household assessments. We will explore the feasibility of recording and analysing telephone interactions between CHWs and households. Once a household has been determined to be COVID-19 free (2 weeks after last symptoms in a diagnosed person) trained qualitative interviewers will conduct interviews with patients, household contacts and caregivers. These in-depth interviews will be limited to a purposive sample of 5 households per group. CHWs and community leaders will also be interviewed.

Assessing SARS-CoV-2 transmission: The research team will conduct SARS-CoV-2 testing with household contacts at baseline and weekly for 1 month. SARS-CoV-2 transmission will be monitored using nasopharyngeal nostril swabs for SARS-CoV-2 GeneXpert PCR and antibody COVID-19 IgG/IgM Rapid serology assays. Nasopharyngeal samples will be collected in a well-ventilated sputum collection space and staff will have adequate protective equipment. Venepuncture will be used to obtain dried blood spots. The test results will be delivered telephonically to household contacts within 24 hours of the test. HHC will complete a daily symptom checklist and symptom data will be collated weekly by the research team. Six months after a positive SARS-CoV-2 antibody, the study nurse will visit the participant household to conduct SARS-CoV-2 serology to assess for the presence of antibodies.

Eligibility of index case:

Inclusion:

Individual >12 years

Able to give assent if <18 years with parental/guardian consent

Able to give consent > 18 years

Self-isolating at home at the time of COVID diagnosis

Exclusion:

<12 years

Unable to give consent

Eligibility of HHC

Inclusion:

Living in the same household as index case

Able to give assent if 12-17 years with parental/guardian consent

Able to give consent \geq 18 years

Exclusion:

Unable to give consent

Table 2: Study procedures

Study participant	Procedure	Baseline	Week	Week	Week	Week
			1	2	3	4
Index						
	ICF		x			
	Demography survey		x			
	Symptom check	x		x	x	x
	Follow up surveys	x		x		x

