 - c. Assessment data of psychosocial functioning (General Health Questionnaire 9 for mood; UCLA Loneliness Scale and a version of the Brief AIDS-Related Stigma scale adapted for COVID-19, at baseline and at week 4);
 - d. Results of serology (pos/neg, no titres) and nasopharyngeal swabs for PCR of HHCs at baseline, and at weeks 1, 2, 3 and 4);
2. Randomisation list
3. Qualitative and quantitative process data on intervention (STOPCOV database)
 - a. Number and duration of calls to households
 - b. transcripts from follow-up calls
 - c. SMS/WhatsApp data
 - d. transcripts from interviews with STOPCov counsellors and intervention/control index and HHC participants
4. Provincial health data(PID; all study participants and household contacts)

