7. ANALYSIS OF PRIMARY STUDY OUTCOMES

7.1. The proportion of SARS-CoV-2 transmitted to HHC of the index COVID19 cases over a 4 week period

SARS-CoV-2 infection in a HHC will be defined as a positive PCR or evolving positive serologic test in a HHC who had a negative PCR or negative serology at baseline. The incidence of SARS-CoV-2 infection in HHC will be calculated as the number of new cases divided by the person time at risk and 95% confidence intervals calculated based on the Poisson distribution adjusted for clustering by household. This incidence as well as the timing to transmission will be analysed using exponential shared frailty models taking the clustering by household into account and allowing for censoring. The start time will be the date of diagnosis of the index case and the event time the date of diagnosis of the HHC using the date of the first positive test based on PCR or serology. Models will include possible confounders including adjustment for baseline values.

7.2. The proportion of transmissions to HHC in the enrolled households of index COVID cases assigned to the infection mitigation intervention arm compared with the households in the enhanced usual care (EUC) arm.

The incidence of SARS-CoV-2 will be estimated for the different study arms and incidence of and timing to SARS-CoV-2 per study arm will be compared by including study arm in the exponential frailty models.

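### Entry rules do not require the index to be the household's first known case, or that any contact be enrolled; homes with an earlier case or no contact can be randomised, and SAP 7.1 does not fully correct for this

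*Protocol*

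**What the plan says.** **Who can be an index.** The Protocol (Approach, Population and Sample) says: "We will consecutively recruit n=120 SARS-CoV-2 positive index patients 12 years and older". The Design text describes "120 consecutively newly diagnosed index patients (GeneXpert SARS-CoV-2 PCR) and up to 8 household contacts will be invited to participate". The eligibility list for the index adds consent or assent and "Self-isolating at home at the time of COVID diagnosis". Nothing asks whether another member of the home has already tested positive.

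**Who can be a contact.** The list asks for "Living in the same household as index case" and consent or assent. Contacts need not be uninfected. The number per home has a ceiling of 8 and no floor. Protocol Table 1 limits contact testing to those aged 12 or over.

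**Order of events.** The schema (Process row) says: "After enrolment, the household will be randomised to the infection mitigation intervention or enhanced usual care messaging". It then describes the baseline questionnaire and the invitation to each occupant. The Design text instead places randomisation after consent is complete, without saying whose consent.

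**Case finding.** The Background says of the mobile service, which is one recruitment source, that "symptomatic individuals or people who have had known contact with a COVID case are screened by a clinician for symptoms", in areas where a case was already known.

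**Analysis.** SAP 7.1 says: "The start time will be the date of diagnosis of the index case". A new infection counts in a contact who had a negative PCR or a negative serology at baseline, and models adjust for baseline values. SAP section 5 keeps every household that entered. SAP section 3 lists as a data source "Provincial health data(PID; all study participants and household contacts").

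**The concern.** Two kinds of home can enter that do not fit the model behind the primary analysis.

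- **A home with an earlier case.** The person labelled index is a later case, and the true first case is labelled a contact. Exposure began before the SAP's time zero, so time to transmission, part of primary objective 1, is measured from the wrong person. Some contacts may already be infected or recovered. STOPCOV arrives after part of the spread, so it has less left to prevent.
- **A home with no enrolled contact.** The index may live alone, all contacts may decline, or all may be under 12. Such a home takes one of the 120 places and adds no person-time to the primary outcome.

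At stake are the accuracy of the Aim 1 timing and incidence results, and some of the information for the Aim 2 comparison.

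**Working it through.** **1. Reproduce the plan's power.** Inputs from the Protocol (Statistical Analysis and sample size; Table 3) and SAP section 3: 120 homes, 6 subjects each, R0 2.5 against 1.5, 1:1 allocation. Alpha is not stated; two-sided 0.05 is assumed because it reproduces the table and one-sided does not.

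- Effective number per arm: n = (homes × 6) / (1 + 5 × ICC) / 2
- Power = Φ( (2.5 − 1.5) / √((2.5² + 1.5²)/n) − 1.96 )

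At ICC 0.90, n = 720/5.5/2 = 65.45. The ratio is 1/√(8.5/65.45) = 2.775, and Φ(0.815) = 79.25% (table: 79.27%). At ICC 0.50, n = 102.86 and power is 93.56% (table: 93.59%). At ICC 0.25, n = 160 and power is 99.13% (table: 99.13%).

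This formula treats every subject as having an event. It is used here only to show the change in power, not to endorse the level.

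**2. Remove homes without a contact.** The numbers 6 and 12 (5% and 10% of 120) are assumptions.

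| ICC | 120 homes | 114 homes | 108 homes |
|---|---|---|---|
| 0.25 | 99.1% | 98.8% | 98.4% |
| 0.50 | 93.6% | 92.4% | 91.0% |
| 0.90 | 79.3% | 77.2% | 74.9% |

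The loss is 4 points at most over these assumptions, and under 1 point at ICC 0.25.

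**3. Contacts already infected in a home with one earlier case.** The plan's control incidence is 0.208, which is 0.208 × 6 = 1.25 infections per 6 contacts. Among the index's 6 contacts are the earlier case (1) and those the earlier case infected, less the index: 1 + 1.25 − 1 = 1.25. That is 1.25/6 = 21%. It assumes that the earlier case had finished transmitting before entry. The floor is the earlier case alone, 1/6 = 17%.

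**4. What the baseline rule removes.** As SAP 7.1 is worded, one negative result is enough.

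| PCR at baseline | Serology at baseline | At risk under 7.1? |
|---|---|---|
| Negative | Negative | Yes |
| Positive | Negative | Yes, though already infected |
| Negative | Positive | Yes, though possibly recovered |
| Positive | Positive | No |

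The rule clearly removes only the last group. A single baseline test also cannot exclude an incubating infection.

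**5. The clock.** In an affected home the time origin is late by the interval between the first case's diagnosis and the index's. The documents give neither that interval nor the share of such homes, so the mean shift cannot be calculated.

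**The case against.** The strongest reply has four parts.

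- **Earlier diagnosed members may be rare.** Protocol Table 1 says that, outside the study, testing of contacts was not routine and was limited to symptomatic people at risk of severe disease. The hotspot account in the Background describes past practice, and a hotspot is an area, not a household. This stands. A reader might infer that many homes in mid-outbreak were randomised; the documents support only that such homes can be.
- **The SAP has safeguards.** Contacts are tested at baseline, models adjust for baseline values, SAP 6.1 reports the time from the index's test to enrolment, and SAP 8.7 describes household exposure from baseline serology. These reduce the problem. None changes the time origin or identifies the first case.
- **Contactless homes are unlikely.** The protocol expects 6 to 8 occupants, and the summary speaks of enrolling index cases together with their contacts after consent. This is fair as to frequency, but no rule secures it, and the schema's order leaves it open.
- **Broad consecutive recruitment is a legitimate choice, and randomisation balances such homes in expectation.** This also stands. A reader might infer that the arm comparison is biased; nothing in the entry rules supports that.

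It is also tempting to put the share already infected at 2.5/6 = 42%, by taking R0 as the number infected. The plan's own incidence of 0.208 gives half that.

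**Conclusion.** The gap is real and its size is unknown. The eligibility lists allow homes with an earlier case, or with no enrolled contact, to be randomised. For Aim 1, timing and incidence are distorted in any home with an earlier case, and the baseline rule is only a partial remedy. For Aim 2, the consequence is dilution and some lost power.

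If 6 to 12 homes had no contact, the power loss would be about 2 to 4 points at ICC 0.90, 1 to 3 points at ICC 0.50, and under 1 point at ICC 0.25. The plan does not single out any ICC as expected. In a home with one earlier case, about 21% of contacts would already be infected on the plan's incidence. The documents do not support a figure for the trial as a whole, because the share of affected homes is not given. The point deserves correction because the remedy is cheap, not because the harm is shown to be large.

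**What to change.** 1. **Entry, before randomisation.** Require at least one consenting contact aged 12 or over. Ask at screening whether another member has already tested positive, and record the date. Then either restrict entry to homes without an earlier known case, or keep such homes and flag them.
2. **SAP, Aim 1.** Flag homes with a household positive dated before the index's diagnosis, using the screening answer and the provincial data already listed. In flagged homes, set the time origin at the first known case, take that person out of the at-risk set, and let contacts enter the risk set at their baseline test (delayed entry). Without delayed entry, moving the clock back would add person-time in which no event could be counted, and so lower the estimated rate.
3. **SAP, 7.2.** Repeat the arm comparison without flagged homes as a sensitivity analysis, and report flagged homes by arm. It should not be assumed that the flag is independent of arm: if contacts were invited after allocation, whose records can be searched may differ between arms.

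The cost is two eligibility lines, one screening question, one record look-up and one further model run. There will be a few more screening failures, and contactless homes are lost to secondary outcomes measured on the index. Earlier undiagnosed cases remain undetected. The SAP cites a protocol dated 15 December 2020, and the protocol ends the study in January 2021, so the entry rules may reach few homes. The SAP changes can still cover all homes if made before sign-off.
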